7.9 Unexpected Adverse Events

The Sponsor will assess all SAEs whether they are expected or unexpected. An unexpected AE is any adverse drug event, the outcome, specificity, or severity of which is not consistent with those noted in the current IB section Reference Safety Information.

7.10 Reporting Serious Adverse Events

Adverse Events classified as serious require expeditious handling and reporting to the assigned Drug Safety contact to comply with regulatory requirements.

Any SAE that occurs while a subject is on study ie, occurs within 30 days of the last study drug administration, regardless of any opinion as to the relationship of the SAE to the study drug,

must be notified to spm² immediately by completing and sending the Serious Adverse Event Report Form via eCRF completion (or email, as required) within 24 hours of becoming aware of the event (Table 5). Any SAE which occurs later than 30 days after the last study drug administration, that the Investigator considers to be related to study drug, must be reported in the same fashion.

Table 5: Contact Information for SAE Reporting

Drug Safety Contract Research Organization:	██████████
SAE E-mail Contact:	██

Abbreviations: SAE = serious adverse event

7.11 Reporting of Serious Adverse Events to Regulatory Authorities

In accordance with the US Code of Federal Regulations, Title 21 CFR Part 312.32, the European Directive 2001/20/EC, and the ICH Guidelines for Clinical Safety Data Management Definitions and Standards for Expedited Reporting, the Sponsor must submit written documentation in the form of an Investigational New Drug (IND) Safety Report or suspected unexpected serious adverse reaction (SUSAR) reports, respectively. The Sponsor should submit to the regulatory authority all safety updates and periodic reports, as required by applicable regulatory requirements. IND Safety Reports/SUSARs are required to be reported within 7 calendar days for life-threatening events and those resulting in death or 15 calendar days for all others. These timeframes begin with the first notification of the IND Safety Reports/SUSARs to the Sponsor or their delegate from the Investigator.

The Sponsor (or their delegate) will determine whether expedited reporting is necessary for SAEs depending on the assessment of seriousness, expectedness and relationship. In case of disagreement between the Investigator and the Sponsor regarding causal relationship, the more conservative assessment will determine the reportability of the case.

The Investigator must ensure they are aware and comply with any additional local reporting requirements. For all SAEs that are related and unexpected, the Sponsor (or their delegate) will assign a case number to be used in all future correspondence regarding the event and can provide a MedWatch or Council for International Organizations of Medical Sciences (CIOMS) form describing the event, for the Investigators to report to their Institutional Review Board (IRB)/Ethics Committee (EC) or other committee. Other SAEs (eg, expected or unrelated SAEs) should be reported per the relevant institution's procedures.

Where required, submission of Safety Updates by the Investigator to Competent Authorities should be handled according to local regulations. Otherwise, periodic safety reports to the regulatory agencies will be handled by the Sponsor (or their delegate). These safety updates will also include SAEs that do not require expedited reporting to the authorities.

Periodically (at least annually), the IB will be updated to include new and relevant safety information. Until such time that an AE becomes identified in the IB, it should be considered unexpected.

7.12 Follow Up Information on an SAE

Collection of complete information concerning SAEs is extremely important. Thus, follow-up information that becomes available as the SAE evolves, as well as supporting documentation (eg, hospital discharge summaries and autopsy reports), should be collected subsequently, if not available at the time of the initial report, and immediately sent using the same procedure as the initial SAE report. The original SAE form must be kept on file at the study site. The Sponsor (or their delegate) will also review SAE reports for missing information and send queries to the site for resolution as appropriate.

Appropriate diagnostic tests should be performed and therapeutic measures, if indicated, should be instituted. Appropriate consultation and follow-up evaluations should be carried out by the Investigator (or designee). An SAE is followed until it is considered resolved, returns to baseline, is chronically ongoing, stabilized or is otherwise explained by the Investigator.

8 STATISTICAL METHODS AND DATA ANALYSIS

Detailed statistical analysis information will be provided separately in the Statistical Analysis Plan (SAP) which will be finalized and signed before the database is locked. The SAP will detail all data handling rules, including the management of missing values and the handling of data for withdrawn subjects. The SAP will also outline protocol deviation criteria. Any deviations to the planned analyses specified or populations defined within the SAP will be justified in writing and presented within the final clinical study report (CSR).

The clinical database lock will occur after all data are reconciled (ie, “cleaned”) for all subjects who receive at least one dose of AFM13. A single CSR will be generated for this study.

An addendum (or addenda) to the CSR will be generated as required to report any data obtained during the Follow-up Assessments.

Where appropriate, tables, listings and figures will be reported by Cohort. Data may be combined and/or summarized by cohort, dose (if different from cohort) and time point.

8.1 Analysis Sets

The study will have three separate cohorts: first cohort (Cohort A) with R/R PTCL subjects with CD30 $\geq 10\%$, second cohort (Cohort B) with R/R PTCL subjects with CD30 $\geq 1\%$ to $< 10\%$, and the third cohort (Cohort C) with R/R TMF subjects with CD30 $\geq 1\%$. All three cohorts will be analyzed independently as described below.

The **full analysis set** (FAS) following the intent to treat (ITT) principle will consist of all subjects who received at least one dose of AFM13. The FAS will be the primary population for all efficacy related endpoints and the primary objective; a sensitivity analysis for all subjects who received at least one dose of AFM13 and had at least one post-baseline efficacy assessment will be conducted to support the results of the primary analysis.

The **safety set** will consist of all subjects who received at least one dose of AFM13 and had at least one post-baseline safety assessment (where the statement that a subject had no AE on the AE eCRF constitutes a safety assessment). The safety set will be the primary population for all safety related endpoints.

The **per protocol set** (PPS) will consist of all subjects in FAS who did not have any major protocol deviations. The primary analysis will be repeated to support the results of the primary analysis on the FAS.

The **pharmacokinetic set** (PK) set consists of all subjects who have at least received one dose of study drug and have at least one post dose PK measurement.

Additional sensitivity analyses might be needed due to the COVID-19 pandemic and those will be defined in the SAP, if deemed necessary.

Subjects who were screened and have signed the ICF but did not receive any treatment will be listed including reason for screen failure and any SAE (this will be recorded in the medical

history). These subjects will not be part of any summary table except for summarizing disposition.

8.1.1 Missing Data and Discontinuation

As this is a non-randomized study design, no imputation of missing values will be done for any analysis except for partial/missing AE dates and concomitant medication dates. Reasons for discontinuation of the study and the study drug will be listed and summarized.

Subjects with missing post-baseline response will be classified as non-responders; however, due to the COVID-19 pandemic additional analyses might be needed and will be specified in the SAP (see [Section 2.1](#)).

8.2 Demographic, Medical History, Prior Medication and Other Baseline Characteristics

Demographic characteristics, prior anti-cancer therapies and surgeries, medical history, prior medication and other baseline data will be listed and summarized using descriptive statistics for continuation data and contingency tables for categorical data. Prior medication/Prior anti-cancer therapies will be coded by WHO Anatomical, Therapeutic, and Chemical (ATC) terms. Medical history will be coded utilizing corresponding Medical Dictionary for Regulatory Activities (MedDRA) System Organ Classes (SOCs) and PTs.

8.3 Study Drug

The number of doses of AFM13 administered over the entire study period will be listed and summarized using descriptive statistics. The time on study drug until last treatment received will be listed and presented by descriptive statistics.

8.4 Concomitant Medication

Concomitant medication and significant non-drug therapies after the start of study drug will be listed and summarized by WHO ATC terms in contingency tables.

8.5 Primary Analysis

8.5.1 Overall Response Rate

Overall response by PET-CT as defined by achieving CR and/or PR assessed by an Independent Review Committee (IRC) utilizing the modified Lugano Classification Revised Staging System for malignant lymphoma ([Cheson, 2014](#)) for Cohorts A and B (PTCL) and the Olsen Criteria ([Olsen, 2011](#)) for Cohort C (TMF). Subjects with missing post-baseline response will be classified as non-responders in the FAS. Results will be presented by percentage rates and 95% CIs. In addition, CR and PR will be presented separately. For all response assessments, swimmer plots will be presented. All response assessments will be listed.

Cohorts A and Cohort C will be analyzed separately and independent from each other at the final analysis. Cohort A may be opened after the interim analysis for all PTCL subjects with $CD30 \geq 1\%$, if Cohort B showed the required ORR (see [Section 8.8.1](#)). The final analysis for

Cohort A will be conducted once all subjects have completed at least two post-baseline disease assessments (ie, ~ 16 weeks post-baseline assessment) to be categorized under the response endpoint or have withdrawn from study drug.

8.6 Secondary Analysis

8.6.1 Efficacy Analyses

Efficacy analyses will be performed based on IRC assessment and Investigator assessment of disease response.

8.6.1.1 Investigator-assessed ORR

The primary analysis will be repeated using the local Investigator-assessed ORR.

8.6.1.2 Duration of Response

The DOR defined as time from first assessment of PR or CR to the first assessment of progressive disease will be summarized by descriptive statistics including median DOR and respective 95% CIs and Kaplan-Meier estimates. DOR will also be listed.

Subjects who started a new anti-lymphoma therapy prior to a documented progressive disease (PD) will be censored at the last disease assessment prior to initiation of new anti-lymphoma therapy. Detailed censoring rules will be described in the SAP.

8.6.2 Safety Analysis

8.6.2.1 Adverse Events

Adverse events, related AEs, SAEs and related SAEs, AEs with NCI CTCAE Grades ≥ 3 , related AEs of NCI CTCAE Grades ≥ 3 , AEs leading to premature discontinuation, interruptions or discontinuation of study drug or dose modification will be analyzed descriptively utilizing corresponding MedDRA SOCs and PTs. NCI CTCAE toxicity grades will be utilized for classifying severity.

8.6.2.2 Safety Laboratory

Safety laboratory results will be graded by NCI CTCAE version v5.0 (or higher). If no grading exists values will be classified into low/normal/high based on laboratory normal ranges. Each parameter will be presented by descriptive statistics at each visit including change from baseline (Screening). Shift tables for CTCAE grades and normal ranges will be presented. All laboratory values will be listed. A separate listing for abnormal lab values (\geq Grade 3, and low/high values) will be presented.

8.6.2.3 Vital Signs

Vital signs will be summarized by descriptive statistics at each visit including change from baseline will be presented and a listing will be provided.

8.6.3 Pharmacokinetic Analysis

The analysis plan for PK assessment for AFM13 in the study will be described in the pharmacokinetic analysis plan. [REDACTED]

Table 6: Pharmacokinetic Parameters

Parameter	Definition
C_{max}	The maximum concentration.
t_{max}	The time to reach maximum concentration.
AUC_{0-t}	The area under the concentration versus time curve from time zero to the sampling time at the last quantifiable concentration (C_t) at t_{last} (the time of the last quantifiable concentration) calculated by the linear up, log down rule.
λ_z	The apparent terminal elimination rate constant, estimated using the negative slope of the least square regression analysis of the natural log concentration versus time data for the terminal linear portion of the curve.
$t_{1/2}$	The terminal half-life, calculated from $\ln 2 / \lambda_z$.
$AUC_{0-\infty}$	The area under the concentration versus time curve from time zero to infinity as the sum of the 2 areas: AUC_{0-t} and AUC_{extrap} , where AUC_{extrap} is calculated as C_t/λ_z .
CL	The clearance calculated as: $Dose/AUC_{0-\infty}$.
V_{ss}	The apparent volume of distribution at steady state calculated as: $Dose/AUC \times (AUMC/UC_{0-\infty} - t_{1/2})$.

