	
[REDACTED]
 
EXCLUSION CRITERIA:
 
1. Subjects with the following subtypes of lymphoma:
 
• T-cell prolymphocytic leukemia• T-cell large granular lymphocytic leukemia• Chronic lymphoproliferative disorder of NK cells• Aggressive NK-cell leukemia• Extranodal NK-/T-cell lymphoma• Indolent T-cell lymphoproliferative disorder of the gastrointestinal tract• Adult T-cell leukemia/lymphoma 
[REDACTED]
 
[REDACTED]
 
[REDACTED]
 
[REDACTED]
 
[REDACTED]
 
[REDACTED]
 
[REDACTED]
 
[REDACTED]
 
[REDACTED]
 
[REDACTED]

--	---

	
[REDACTED]
 
[REDACTED]
 

[REDACTED]	[REDACTED]	

[REDACTED]	[REDACTED]	

[REDACTED]	[REDACTED]	

[REDACTED]	[REDACTED]	

[REDACTED]	[REDACTED]	

 
[REDACTED]
 
[REDACTED]
 
[REDACTED]
 
[REDACTED]
 
[REDACTED]
 
[REDACTED]
 
[REDACTED]
 
[REDACTED]
	[REDACTED]	[REDACTED]	[REDACTED]	[REDACTED]	[REDACTED]	[REDACTED]	[REDACTED]	[REDACTED]	[REDACTED]	[REDACTED]
[REDACTED]	[REDACTED]										
[REDACTED]	[REDACTED]										
[REDACTED]	[REDACTED]										
[REDACTED]	[REDACTED]										
[REDACTED]	[REDACTED]										
Investigational product, dosage and mode of administration	AFM13 will be administered intravenously at a dose of 200 mg. Subjects will be treated weekly until disease progression, unacceptable toxicity, Investigator discretion, or withdrawal of consent.										
Criteria for evaluation	Anti-tumor Activity: 
• Cohorts A and B (PTCL): FDG-PET and CT scans• Cohort C (TMF): peripheral blood samples, CT scans (or										

subjects with CD30 positive $\geq 1\%$ to $<10\%$ by IHC, and Cohort C (TMF) subjects with CD30 expression $\geq 1\%$ by IHC. All three cohorts will be analyzed independently as described below.

Analysis Sets:

The full analysis set (FAS) following the intent to treat principle will consist of all subjects who received at least one dose of AFM13. The FAS will be the primary population for all efficacy related endpoints and the primary objective; an additional sensitivity analysis for all subjects who received at least one dose of AFM13 and had at least one post-baseline efficacy assessment will be conducted to support the results of the primary analysis.

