6 STUDY MEDICATION AND ADMINISTRATION

Affimed will supply AFM13 study drug as a sterile lyophilized powder for reconstitution for intravenous (IV) infusion (Table 3). Full details on the preparation and administration of AFM13 are provided in the Pharmacy Manual for the study.

The Investigator shall take responsibility for the study drug and shall take all steps to maintain appropriate records and ensure appropriate supply, storage, handling, distribution, and usage of study drug in accordance with the protocol and any applicable laws and regulations.

The Quality Control Standards and requirements for AFM13 study drug are described in separate release protocols/Certificate of Analysis.

Please refer to the current version of the IB for additional information on the physical, chemical, and pharmaceutical properties of AFM13.

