4.2 Secondary efficacy endpoints

The secondary efficacy endpoints of this study are:

- CR rate, PR rate, and CT-based ORR as confirmed by an IRC as assessed by the modified Lugano Classification (Cheson, 2014) for Cohorts A and B (PTCL) based on CT and after at least 8 weeks from the first assessment by Olsen Criteria (Olsen, 2011) for Cohort C (TMF).
- ORR-2 confirmed by Investigator assessment as assessed by the modified Lugano Classification (Cheson, 2014) for Cohorts A and B (PTCL) and after at least 8 weeks from the first assessment by Olsen Criteria (Olsen, 2011) for Cohort C (TMF).
- DOR as assessed by the modified Lugano Classification (Cheson, 2014) for Cohorts A and B (PTCL) and after at least 8 weeks from the first assessment by Olsen Criteria (Olsen, 2011) for Cohort C (TMF) based on IRC assessment.
- Assessment of non-compartmental PK parameters including C_{max} , AUC, volume of distribution at steady state (V_{ss}), half-life ($t_{1/2}$).
- Incidence of subjects who develop anti-drug antibodies (ADA) during treatment in blood and their neutralizing potential.
- QOL as measured by European Quality of Life 5-Dimensional (EQ-5D) for Cohorts A and B, and by Skindex-29 for Cohort C.

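### Protocol Table 6, as printed, subtracts the terminal half-life in the Vss formula where half the infusion duration belongs; taken literally, Vss is biased low for any infusion shorter than two half-lives

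*Protocol*

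**What the plan says.** Protocol Section 8.6.3, Table 6, lists the PK parameters and how each is derived. The relevant rows are:

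- Half-life: "The terminal half-life, calculated from" ln2/λz.
- Clearance: "The clearance calculated as" Dose/AUC0-∞.
- Vss, three rows below the half-life: "The apparent volume of distribution at steady state calculated as" an expression that reads "Dose/AUC \times (AUMC/UC_{0-\infty} - t_{1/2" in the text available, with the closing bracket following. The second AUC has lost its first letter. AUMC is not defined in the table, and no symbol for infusion duration appears.

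The drug is supplied as a "sterile lyophilized powder for reconstitution for intravenous (IV) infusion" (Protocol Section 6), and the synopsis also gives the route as intravenous.

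Vss is a named secondary parameter. SAP Section 4.2 lists "Assessment of non-compartmental PK parameters including" Cmax, AUC, "volume of distribution at steady state" and half-life, and Protocol Table 2 names the same four.

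Protocol Section 8.6.3 leaves the PK analysis to a separate pharmacokinetic analysis plan. SAP Section 8.8.1 leaves the PK parameter summaries to a separate non-compartmental report. Neither is among the documents, and the SAP does not restate the Vss formula.

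**The concern.** The bracket in a Vss formula should contain the mean residence time of drug in the body. After an infusion, AUMC/AUC also includes the average time the drug spent waiting to be infused, and that part must be removed. The terminal half-life describes how the drug leaves the body. It is not an input time and has no role in this correction.

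If the formula were programmed as printed, one of the four PK parameters named in the secondary endpoint would be wrong. The error would not be a constant factor that could be scaled out, because it depends on each subject's half-life and infusion time. Some values could be negative, which is impossible for a volume.

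**Working it through.** The plan states no numerical Vss, so there is no figure to reproduce. The check is on the formula.

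**Inputs from the documents.** CL = Dose/AUC0-∞, t1/2 = ln2/λz and the printed Vss expression (Protocol Table 6); intravenous infusion (Protocol synopsis and Section 6). The dose cancels in the ratio below.

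**Inputs that must be assumed.** AFM13's half-life and this study's infusion duration T are not visible. The only infusion times shown are for the earlier study AFM13-102 (Protocol Table 1): 4 hours, or in one cohort a loading dose followed by continuous infusion over 5 days. I use T from 0 to 8 h and half-lives from 4 to 48 h, with linear kinetics, central elimination and a constant infusion rate.

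**Step 1: the correct form.** For an infusion of length T, AUMC/AUC = MRT + T/2. Hence Vss = CL × MRT = CL × (AUMC/AUC − T/2).

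**Step 2: ratio of printed to true.** The printed bracket is MRT + T/2 − t1/2, so

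printed/true = 1 + (T/2 − t1/2)/MRT.

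This is below 1 exactly when T < 2 × t1/2, equal to 1 at T = 2 × t1/2, and above 1 beyond that.

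**Step 3: one compartment.** Here MRT = t1/2/ln2, which gives

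printed/true = 1 − ln2 + ln2 × T/(2 × t1/2).

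- T → 0: 1 − 0.693 = 0.307, or 69% too low.
- Ratio 0.5: T/t1/2 = 2 × (1 − 0.5/0.693) = 0.557, or 50% too low.
- T = t1/2: 0.307 + 0.347 = 0.653 after rounding, or 35% too low.

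Printed/true over the assumed range:

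| T (h) | t1/2 = 4 h | 6 h | 12 h | 20 h | 48 h |
|---|---|---|---|---|---|
| 1 | 0.393 | 0.365 | 0.336 | 0.324 | 0.314 |
| 4 | 0.653 | 0.538 | 0.422 | 0.376 | 0.336 |
| 8 | 1.000 | 0.769 | 0.538 | 0.445 | 0.365 |

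**Step 4: more than one compartment.** MRT is then at most t1/2/ln2, so when T < 2 × t1/2 the proportional loss is at least the one-compartment loss at the same T and t1/2. The result is negative when MRT + T/2 < t1/2. That cannot happen in one compartment, where MRT exceeds t1/2. Three illustrative two-compartment cases with T = 4 h and a central volume of 3 L, with CL = central volume × k10:

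| k10, k12, k21 (per h) | t1/2 (h) | MRT (h) | CL (L/h) | True Vss (L) | Printed Vss (L) |
|---|---|---|---|---|---|
| 0.1, 0.05, 0.05 | 23.67 | 20.00 | 0.3 | 6.0 | 0.3 × (22.00 − 23.67) = −0.5 |
| 0.2, 0.1, 0.03 | 35.89 | 21.67 | 0.6 | 13.0 | 0.6 × (23.67 − 35.89) = −7.3 |
| 0.3, 0.05, 0.02 | 40.78 | 11.67 | 0.9 | 10.5 | 0.9 × (13.67 − 40.78) = −24.4 |

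**Step 5: check of the correction.** Numerical integration of the infusion curves with T/2 in place of t1/2 returned the true volume each time: 5.0 L in one compartment, and 6.0, 13.0 and 10.5 L in the three cases above.

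**The case against.** **The symbol may have been misread.** The same bracket has lost a letter from AUC, so this cell was not read cleanly. The correct term is itself a time divided by two and could have been misread as t1/2. This stands as a reason to look at the source page first. It does not clear the text as it reads now: the symbol is well formed and identical to the one in the half-life row. If the page does show an infusion-time term, Table 6 still defines neither that term nor AUMC.

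**Table 6 may not govern the calculation.** A separate PK analysis plan and non-compartmental report will carry the analysis, and Protocol Section 9.1 names WinNonLin Pro or equivalent. The reported Vss may therefore be right in practice. That also stands, but no visible text corrects Table 6. If the PK plan uses another formula, the two documents disagree; if it copies Table 6, the results are biased.

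**The size is not known.** A reader might infer that Vss would be at least halved, or wrong for every subject. The documents do not support either as an unconditional statement. In one compartment a loss of half or more needs T no longer than about 0.56 × t1/2, for example a half-life of about 7.2 h or more with a 4 h infusion. The bias vanishes at T = 2 × t1/2 and reverses beyond it. Likewise, negative values are possible only with multi-compartment disposition, and the cases above use invented rate constants.

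**The consequence is limited.** In the visible text Vss feeds no test or decision rule, and it can be recalculated later from concentrations and infusion times. This is accepted.

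**Conclusion.** As printed, the Vss definition in Protocol Table 6 is wrong for a drug given by infusion: it subtracts the terminal half-life where T/2 belongs. The direction follows from algebra alone: Vss is too low whenever the infusion is shorter than two terminal half-lives. The size rests on quantities the documents do not show. In a one-compartment model it runs from 69% too low at the bolus limit, through 35% at T = t1/2, to zero at T = 2 × t1/2. With multi-compartment disposition the loss is at least as large for the same T and t1/2, and the value can be negative.

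The conclusion is subject to confirmation that the source page really prints t1/2. It does not show that reported values will be wrong, since the PK analysis plan is unseen. The primary ORR analysis, Cmax, tmax, AUC, λz, t1/2 and CL do not use this formula and are unaffected. The point is worth correcting because Vss is a named secondary parameter and the correction is almost free.

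**What to change.** 1. Check the Vss row of Table 6 against the source page.
2. If the symbol is t1/2, replace the row with Vss = CL × (AUMC0-∞/AUC0-∞ − T/2), where T is the subject's actual infusion duration. Writing CL also makes clear that the leading AUC is AUC0-∞.
3. Define AUMC and T in Table 6, whatever the source page shows.
4. Confirm that the PK analysis plan and the non-compartmental report use the same formula. T/2 is exact only for a constant-rate infusion, and SAP Section 8.5.1 expects some interrupted infusions, so the PK plan should state how those are handled.

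The cost is one corrected formula, two definitions and a consistency check. It changes no design feature or sample size.
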